5.2 Inclusion Criteria

Patients are eligible for the study if they meet the following inclusion criteria:

- 1) Written informed consent before any study related procedures are performed
- 2) Inpatients or outpatients referred by their providers for ECT treatment and eligible for ECT treatment
- 3) Males or females at least 21 years of age, but no older than 75 years of age
- 4) Meet DSM-5 criteria for a Major Depressive Episode as determined by both:
 - a clinician's diagnostic evaluation and
 - confirmed by interview using the Mini International Neuropsychiatric Interview (MINI 7.0.2)
- 5) A current depressive episode that has lasted a minimum of two weeks
- 6) Meet all of the following criteria on symptom rating scales at screening:
 - Montgomery Asberg Depression Rating Scale (MADRS) score >20
 - Young Mania Rating Scale (YMRS) ≤ 5
 - Montreal Cognitive Assessment (MoCA) of ≥ 18
- 7) Have had ≥ 2 adequate trials of antidepressants/augmentation strategies during their lifetime. An adequate trial is defined as 4 weeks of a medication at minimum FDA approved dose. This will be equal to a trial rating of 3 or greater.
- 8) In the opinion of the investigator, the patient is willing and able to comply with scheduled visits, treatment plan, and other trial procedures for the duration of the study

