7.1 Screening Period (Maximum of 28 days)

- Informed Consent: An investigator and/or other delegated study team member will discuss all risks and benefits of participation and review the study visit schedule with the patient. The patient will sign the informed consent form prior to any study procedures being performed.
- Assessment of Inclusion/Exclusion Criteria
- Demographics
- Medical History, including psychiatric history and history of neurological conditions
- Psychiatric Medication Log
- Somatic Therapies Log
- Clinical Psychiatric Evaluation
- Diagnostic evaluation by investigator
 - Meets DSM-5 criteria for MDD, but does not meet DSM-5 criteria for Bipolar Disorder, Schizophrenia, Schizophreniform disorder, schizoaffective disorder, mental retardation, Pervasive Development Disorder
 - o No psychotic features during the current depressive episode
 - Verify current depressive episode has lasted at least 4 weeks
 - Verify that patient has had at least two adequate trials of antidepressant therapy
- Urine pregnancy test for females of child bearing potential
- Diagnostic Interview
 - o MINI 7.0.2
- Clinician Rated Scales
 - MADRS
 - o YMRS
- Cognitive Assessments
 - MoCA

If patients meet eligibility criteria, they will be randomized into either the ECT or ketamine arm via a secure electronic data management system. Randomization can be done by study staff after the screening visit. Depending on which arm the patient is randomized to, the study nurse will schedule them for their Baseline/Visit 1 according to the site's clinical or research schedule.

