8.5 Pregnancy

All pregnancies should be reported to C5Research within 24 hours of becoming aware of the pregnancy.

• Maternal exposure – If a patient becomes pregnant during the course of the study, study treatment will be continued or discontinued per investigator discretion. If any pregnancy occurs in the course of the study, the investigator

- must inform C5Research within 24 hours of awareness of the pregnancy.
- Paternal exposure There are no known risks regarding fathering a child while receiving either ECT or ketamine treatment. But, since there is limited data on ketamine in pregnancy it is advised that patients practice adequate birth control while in the study.

9. Statistical Plan

The key exposures of this study are alternate day ECT treatment and twice a week ketamine infusion. We will conduct an intention to treat (ITT) analysis. A sensitivity analysis will be performed on the modified intention-to-treat (mITT) population defined as a randomized patient having at least one treatment and one valid QIDS- SR16 measurement during the acute treatment phase. Percent of responders is the primary outcome in this study. A responder is defined as a subject with a ≥50% decrease from baseline in the primary endpoint (QIDS-SR-16).

Multiple imputations may be implemented to achieve completeness of the data. In an unlikely case that missing data are non-ignorable, pattern-mixture modeling will be applied.

As a general principle, the statistical analysis will follow the pre-specified statistical analysis plan (SAP). The SAP will be finalized prior to the end of the study. The SAP will address how missing data will be handled.

The primary outcome measure of response rate will be compared between ketamine and ECT using a chi-square test. A multivariable logistic regression model will be constructed, to account for potential heterogeneity of treatment effect caused by confounding variables. A similar analytic strategy will be applied to evaluate cognitive function and quality of life.

Sample size

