Since the QIDS-SR16 score itself is repeatedly measured over time, a linear mixed-effects model will be applied to estimate its trajectories of the two groups during the acute treatment phase. The model will include measurement time, treatment group, their interaction, and site as fixed effects, and a Gaussian random intercept at the patient level. Baseline patient characteristics with statistically significant differences between the two groups may be also included as fixed effects if deemed necessary. The covariance matrix of the repeated measurements within each patient will be selected from the candidates of compound symmetric, first-order autoregressive (AR1), Toeplitz, and unstructured structures using the information criterion. Least-square estimates will be derived to estimate the QIDS-SR16 mean at each visit by group, and corresponding linear contrasts can be used for group comparison at each visit. Since the responders will be further followed at months 1, 3 and 6 after the acute phase, another linear

mixed-effects model with the same formation will be applied to the subgroup of responders for their longitudinal QIDS-SR-16 data until the end of the follow up phase. The model for the change of QIDS-SR-16 score will include the score changes as the dependent variable and further include the baseline QIDS-SR-16 score as a covariate. For the other continuous secondary endpoints measured longitudinally, their analyses will follow the analysis of the QIDS-SR-16 score. These endpoints include various patient and clinician rated scales for depression, suicidality, and cognitive function (e.g., MADRS and YMRS).

For the cross-sectional endpoints such as the MoCA rating assessed at the end of treatment visit, linear regression will be used to analyze and compare the data between the two groups. Generalized linear regression (e.g., logistic regression or ordinal logistic regression) will be applied to binary or multi-categorical outcomes, depending on the variable type of the outcome.

Analysis of safety endpoints. Mortality will be summarized as percentage by group, and the chi-squared test will be used to compare the mortality rates between the two groups. If the expected number of deaths is small, the Fisher's exact test will be used instead. The other dichotomous safety outcomes such as the unexpected adverse events, adverse events causing treatment discontinuation and serious adverse events will be analyzed in the same manner.

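### The end-of-treatment MoCA comparison names no term for the screening MoCA that every eligible patient has, so it may be less precise than the collected data allow.

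*SAP*

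**What the plan says.** The SAP, under Analysis of secondary endpoints, puts MoCA in a class of its own: "For the cross-sectional endpoints such as the MoCA rating assessed at the end of treatment visit, linear regression will be used" to compare the two groups. It names no screening MoCA and no site term, and it does not say whether the outcome is the EOT score or the change from screening.

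The protocol collects MoCA twice by the end of acute treatment. Section 5.2 introduces its rating-scale thresholds with "Meet all of the following criteria on symptom rating scales at screening" and lists "Montreal Cognitive Assessment (MoCA) of ≥ 18". Section 7.1 places the test in the screening period, before randomisation. Section 7.4 and both arms' Schedules of Events repeat it at the EOT visit.

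Elsewhere in the same part of the SAP, covariates are named. For the QIDS-SR-16 mixed model: "The model will include measurement time, treatment group, their interaction, and site as fixed effects". The model for QIDS-SR-16 change will "further include the baseline QIDS-SR-16 score as a covariate".

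Protocol Section 9, after describing a multivariable logistic model for response, adds: "A similar analytic strategy will be applied to evaluate cognitive function and quality of life". It lists no covariates.

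**The concern.** Effects on memory and cognition are Specific Aim 2. Treating EOT MoCA as cross-sectional passes over a pre-randomisation score on the same instrument, which the eligibility rule guarantees for every properly enrolled patient. A baseline value of the outcome is usually the most useful covariate available, and the SAP uses one for QIDS-SR-16 change.

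Two things are at stake. The first is precision: the interval for the arm difference is wider than it need be, by an amount that depends on how closely screening and EOT scores are correlated. The second is specification. Under the present wording one analyst could fit the EOT score on treatment alone, another the change score, and a third the EOT score adjusted for screening. Each could claim to follow the plan, and the estimates would differ. The SAP's own summary of changes says version 2.0 was drafted at the end of the study, and the trial is open-label, so it is worth settling the model in writing.

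**Working it through.** **The plan's own figure.** There is none to reproduce. Neither document gives a standard deviation, target difference, correlation or power for MoCA.

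**Inputs from the documents**
- 400 patients randomised 1:1 and 15% attrition (SAP, Sample size justification): 400 × 0.85 / 2 = 170 per arm.
- 4 to 6 sites (Protocol synopsis). Taking 6 gives 5 site terms.
- Longest gap from screening to EOT: 28 days of screening, 7 days to randomise once eligible, 35 days of treatment (5 weeks), and 3 days to the EOT visit. 28 + 7 + 35 + 3 = 73 days, taking Visit 1 straight after randomisation.

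**Assumptions**
- Within-arm correlation ρ between screening and EOT MoCA of 0.2, 0.3, 0.5 or 0.7.
- Two-sided 5% test.
- True differences d of 0.3 SD and 0.2 SD.
- The site terms are charged their degrees of freedom but credited with no variance reduction.

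**Formulas**
- The variance of the adjusted difference is about (1 − ρ²) times the unadjusted variance.
- 95% CI half-width in SD units = t(0.975, df) × √[(2/170)(1 − ρ²)]. The df are 340 − 2 = 338 unadjusted, and 340 − 2 − 1 − 5 = 332 with screening MoCA and 5 site terms.
- Equivalent unadjusted n per arm = 170 / (1 − ρ²).
- Power from the noncentral t distribution, with noncentrality d / √(1 − ρ²) × √(170/2).

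**Unadjusted.** √(2/170) = 0.1085 and t = 1.967, so the half-width is 0.2134 SD.

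**Adjusted**

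| ρ | 1 − ρ² | Half-width (SD) | Narrower by | Equivalent n per arm | Power, d = 0.3 | Power, d = 0.2 |
|---|---|---|---|---|---|---|
| unadjusted | 1 | 0.2134 | – | 170 | 78.8% | 45.2% |
| 0.2 | 0.96 | 0.2091 | 2% | 177 | 80.4% | 46.7% |
| 0.3 | 0.91 | 0.2035 | 5% | 187 | 82.4% | 48.7% |
| 0.5 | 0.75 | 0.1848 | 13% | 227 | 89.0% | 56.5% |
| 0.7 | 0.51 | 0.1524 | 29% | 333 | 97.1% | 73.1% |

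The site terms cost less than 0.1 percentage point of power.

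**Chance imbalance.** A screening difference between arms at its 95% limit is 0.2134 SD. Of this, ρ × 0.2134 passes into the unadjusted EOT difference: 0.04, 0.06, 0.11 or 0.15 SD at ρ = 0.2, 0.3, 0.5 or 0.7. Adjustment removes that component. It averages to zero over randomisations, so it is not bias.

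**Which row is likely?** Cutting the screening score off at 18 restricts its range, and the gap can reach about 73 days. Both tend to lower ρ, so the upper rows deserve at least as much weight as the lower ones.

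**The case against.** The best reply is that the SAP is silent rather than wrong. Linear regression admits covariates, and Protocol Section 9 extends its multivariable approach to cognition. The SAP's summary of changes also describes cognitive measures as following the longitudinal QIDS-SR-16 or MADRS analyses. All of this is fair, but none of it supplies the missing term. Section 9 names no covariate. The operative SAP text puts EOT MoCA under cross-sectional regression, and the only baseline score that the longitudinal text names is QIDS-SR-16.

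The second reply is about size, and it stands. MoCA is one of about 20 secondary rows in SAP Table 1, with no stated target difference. At correlations of 0.2 to 0.3 the interval narrows by only 2% to 5%. No precision gain from site has been shown, and Protocol Section 5.4 does not mention stratification by site.

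A reader might infer three stronger things that the documents do not support.
- *That the MoCA comparison is biased or invalid.* It is not; randomisation protects it.
- *That every continuous secondary endpoint should be adjusted for a pre-treatment value.* CADSS and BPRS are given after treatment at Visit 1 (Protocol Sections 4.2 and 7.2), so their first score is already post-treatment and adjusting for it could remove part of the effect. Section 4.2 also takes the EOT visit as baseline for the follow-up analyses. In the trajectory models, Visit 1 may itself be an outcome row.
- *That the SAP's optional covariate rule damages this analysis.* That rule reads: "Baseline patient characteristics with statistically significant differences between the two groups may be also included as fixed effects if deemed necessary". It is written for the mixed models, not for the MoCA regression. In a simplified simulation of a single EOT comparison, it changed power by −0.1 to +0.4 percentage points against no extra covariate (Monte Carlo error about 0.4), with type I error of 4.7% to 5.0%.

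**Conclusion.** The point holds for the EOT MoCA analysis and no further. The SAP leaves unstated whether a baseline score already in hand will be used. If it is not used, the comparison is valid but less precise than it could be. The loss is small if screening and EOT scores are weakly correlated (78.8% against 80.4% to 82.4% power for 0.3 SD at ρ of 0.2 to 0.3) and substantial only if they are strongly correlated (97.1% at 0.7).

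These figures rest on 170 evaluable patients per arm and on assumed correlations and differences that the documents do not give. The case for acting does not depend on the larger figures: the adjustment costs almost nothing, and naming it closes the choice of model. MoCA is a secondary endpoint, and neither the primary non-inferiority analysis nor the sample size is affected.

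**What to change.** State in the SAP that EOT MoCA will be analysed by analysis of covariance, with the EOT score as outcome and treatment, screening MoCA and site as terms, and that the unadjusted difference will be reported alongside. Site is included for consistency with the SAP's mixed models, not for an expected gain in precision.

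Confine the change to MoCA. Extending it to other secondary scales would need a check, scale by scale, of whether a true pre-treatment value exists and which visit serves as baseline.

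The cost is a short, dated SAP amendment. Screening MoCA and site are already recorded. Because version 2.0 was drafted at the end of an open-label study, the amendment should be made without reference to outcomes by arm and should say so.

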ELEKT–D: Electroconvulsive therapy (ECT) vs. ketamine in patients with treatment resistant depression (TRD)

Statistical Analysis Plan

Version 2.0 07/01/2022

ELEKT-D is an open label, multi-center clinical trial to compare electroconvulsive therapy (ECT) with ketamine (KET) in patients with treatment resistant depression (TRD). The specific study aims include:

- Aim 1: to investigate the comparative effectiveness of ECT and ketamine on measures of depression.
- Aim 2: To investigate the relative impact of ECT and ketamine on measures of memory and cognitive function.
- Aim 3: To investigate the relative impact of ECT and ketamine on patient reported QoL measures after acute treatment and at follow-up over six months.

Table 1 below lists the primary, secondary and safety endpoints measured from the study participants. More details and the measurement schedules of these endpoints are described in the study protocol.

Analysis of baseline characteristics. The analysis will be based on the randomized population (i.e., all participants randomized). Participant characteristics at baseline will be summarized as descriptive statistics (mean, standard deviation [SD], median, inter-quartile range, or range for continuous data, and count and percentage for categorical data). The baseline characteristics will be compared between the two study groups using the t-test, the Wilcoxon rank sum test, or the chi-squared test as appropriate.

Analysis of primary endpoint. The primary endpoint of the trial is treatment response, which is defined as $a \ge 50\%$ decrease in QIDS-SR-16 scores from the baseline visit/visit 1 to the end of treatment visit in the acute phase. The study hypothesis is that the response rate of ketamine is non-inferior to ECT with a margin of -10%, that is,

$$H_0: P_k - P_e \le -10\%$$
 vs. $H_1: P_k - P_e \ge -10\%$

where P_k represents the response rates in the ketamine group, and P_e represents the response rate in the ECT grou; H_0 and H_1 denote the null and alternative hypotheses, respectively. The primary endpoint of treatment response will be summarized as proportions, along with 95% confidence intervals, for each treatment group. The Farrington-Manning score test will be then used to compare the response rates between ECT and KET at an inferiority margin of -10% (ketamine minus ECT) and a one-sided type I error of 0.025. The difference of the two response rates will be also reported with the 95% confidence interval.

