Sample size justification. For the outcome measure of QIDS-SR16 in TRD patients in standard anti-depressant analyses, an overall response rate of 47% was reported in the STAR*D study [1]. Zarate et al. showed that a 71% response rate of ketamine on HAMD-21 was associated with patients with major depression [2]. Murrough et al. reported a 64% response rate of ketamine on MADRS in patients with TRD [3]. Other studies revealed response rates of ketamine ranging from 50% to 90% in patients with TRD [4-14]. Janicak et al. reported a 56% response rate of ECT on HAMD-24 in patients of major depression [15]. Our preliminary internal data showed 45.8% patients as responders in the ketamine group, and 45.1% patients as responders in the ECT group, using clinician rated MADRS scales. The patients in the ketamine group were resistant to ECT treatment and still had a comparable response rate as ECT. For the ELEKT-D study, patients do not have to be ECT resistant, and hence the ketamine response rate is expected to be even higher. Based on the above data from the previous studies and our pilot study, we assume a 50% response rate for ECT patients. At a non-inferiority margin of 10% (i.e. response rate of ketamine is at most 10% lower than ECT) and a one-sided alpha value of 0.025, a total sample of 346 is needed to provide 80% power using the Farrington-Manning score test of risk difference if the actual difference is +5% (i.e. response rate of ketamine is 5% higher than ECT). If the actual difference is +10%, the statistical power would increase to 96.4% with the same sample size; if the non-inferiority margin is reduced to 5%, then the power will be 80.3%. Assuming an attrition rate of 15%, a total number of 400 subjects (200 per treatment group) are then required.

References

[2] Zarate CA Jr., Singh JB, Carlson PJ, et al. A randomized trial of an N-methyl-D-aspartate antagonist in treatment-resistant major depression. Arch Gen Psychiatry. 2006; 63(8):856–864.

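### The four dichotomous safety endpoints are compared by percentages and a p-value only, with no effect estimate or interval, so a doubling of an uncommon harm would usually read as non-significant with no stated bound on the excess

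*SAP*

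**What the plan says.** The SAP, under Analysis of safety endpoints, states: "Mortality will be summarized as percentage by group, and the chi-squared test will be used to compare the mortality rates between the two groups". It adds: "If the expected number of deaths is small, the Fisher's exact test will be used instead". Unexpected AEs follow the same method, and "adverse events causing treatment discontinuation and serious adverse events will be analyzed in the same manner". That is the whole between-arm plan for these four endpoints. The section gives no risk difference, risk ratio, interval or margin, and no significance level. It does not say how small an expected number triggers Fisher's test, and it names no analysis population.

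Nothing elsewhere fills the gap. Section 9 of the protocol (Statistical Plan) describes no safety analysis. The SAP's logistic regression for binary outcomes sits under secondary endpoints, and its mixed models for safety cover vital signs only.

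The primary endpoint is treated differently. Under Analysis of primary endpoint the SAP plans a 95% interval for each arm's response rate, and then: "The difference of the two response rates will be also reported with the 95% confidence interval".

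Protocol section 8.3 collects SAEs from consent to the one-month call for non-responders, but through the applicable follow-up visits, up to Month 6, for responders.

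**The concern.** The trial is sized for a 10-point non-inferiority margin on an event expected in about half the patients. A test of equality on an event seen in a few percent has little power at that size, so a non-significant p-value says little about how much more harm one arm might carry. If ketamine is non-inferior on response, harms become an important part of the choice between treatments. For these four endpoints the planned output would not show the reader what excess is still compatible with the data.

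The SAP recognises low power for its subgroup interaction tests and labels them hypothesis generating. It attaches no such caution to the safety tests.

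**Working it through.** **Inputs from the documents.** The SAP's sample size section says "a total number of 400 subjects (200 per treatment group) are then required", with 15% attrition assumed, so 400 × 0.85 / 2 = 170 per arm as a lower case. The tests are chi-squared, or Fisher when few events are expected.

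**Assumptions.** Two-sided 0.05; Fisher when the expected count per arm is below 5; base rates from 0.5% to 10%. The documents state none of these.

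**The plan's own figure.** No power or precision is given for any safety endpoint. The primary-endpoint figure reproduces. With 173 per arm, 55% v 50%, margin 10 points and one-sided 0.025:

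- SE under the alternative = √[(0.55×0.45 + 0.50×0.50)/173] = 0.0536.
- SE under the null (restricted rates about 0.475 and 0.575) = √[(0.2494 + 0.2444)/173] = 0.0534.
- Power = Φ[(0.15 − 1.96×0.0534)/0.0536] = Φ(0.84) = 80%, as stated for 346 patients.

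**Power of the safety tests.** Power is the sum, over all pairs of event counts (i, j), of Bin(i; n, p₀) × Bin(j; n, p₁) for pairs where the test rejects. Missed = 1 − power.

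| True rates | Missed, 200 per arm | Missed, 170 per arm |
|---|---|---|
| Doubling: 1% v 2% | 95% | 97% |
| 2% v 4% | 80% | 85% |
| 3% v 6% | 70% | 74% |
| 5% v 10% | 53% | 58% |
| Tripling: 1% v 3% | 80% | 86% |
| 2% v 6% | 46% | 53% |
| 3% v 9% | 27% | 34% |
| 5% v 15% | 7% | 11% |

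At 200 per arm, power passes 50% at a base rate of about 5.3% for a doubling and about 1.8% for a tripling. With Fisher used throughout, these points move to 6.1% and 2.2%. The cut-off matters most at the lowest rates: 0.5% v 2% is missed 90% of the time under the assumed rule and 75% with chi-squared alone.

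**What an interval would add.** Take 10/200 v 4/200 (5% v 2%).

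- The expected count is 14/2 = 7 per arm, so chi-squared applies. The pooled rate is 14/400 = 0.035, and z = 0.03/√(0.035×0.965×2/200) = 0.03/0.0184 = 1.63, so p = 0.10.
- The Wilson limits are 2.74% to 8.96% and 0.78% to 5.03%.
- Newcombe lower limit: 3.0 − √[(5 − 2.74)² + (5.03 − 2)²] = 3.0 − 3.8 = −0.8 points.
- Newcombe upper limit: 3.0 + √[(8.96 − 5)² + (2 − 0.78)²] = 3.0 + 4.1 = +7.1 points.

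The p-value alone reads as no significant difference. The interval shows that an excess of up to 7 points has not been excluded. By the same method, 6 v 2 events (Fisher p = 0.28) gives −1.0 to +5.5 points, and 0 v 0 still leaves −1.9 to +1.9.

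**The case against.** Percentages with a test are conventional for safety. With the arm denominators anyone can calculate the interval, so no data are lost and no result is biased. An interval adds no power; it displays the same uncertainty. All of that is true, and it is why the point is modest. It does not explain why the SAP pre-specifies the informative estimate for response and leaves it to the reader for harms.

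A reader might go further in three ways that the documents do not support.

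- **That the SAP would take p > 0.05 as equal safety.** It makes no such claim and sets no safety margin. The risk lies in how the result is later read.
- **That any doubling or tripling of a harm would be missed.** The table contradicts this: 3% v 9% is detected 73% of the time and 5% v 15% 93%. A doubling from 10% to 20% is also detected, 81% of the time.
- **That no between-arm safety estimate is planned at all.** Vital signs get mixed-model means by group. Side-effect, dissociation, suicidality, memory and cognition scales are secondary endpoints, and the SAP gives its continuous secondary endpoints mixed models or regression. The gap is confined to the four dichotomous endpoints.

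A further objection is that a crude SAE risk difference would inherit the unequal collection windows of responders and non-responders. That stands, and the fix deals with it.

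**Conclusion.** The point holds for mortality, unexpected AEs, AEs causing discontinuation and SAEs: the SAP plans a test of equality with no effect estimate or interval. At 200 per arm a non-significant result is the usual outcome for a doubling from a base rate up to about 5%, or a tripling from one below about 2%. Above those rates detection is more likely than not.

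The thresholds rest on the assumed level, Fisher cut-off and harm rates. The absence of an interval does not depend on them. The primary analysis is unaffected; this is a modest improvement in how the safety comparison is reported and read.

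**What to change.** Replace the comparison for these four endpoints in the SAP's safety section with text along these lines:

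*For mortality, unexpected AEs, AEs causing treatment discontinuation and SAEs, the between-arm comparison is the risk difference (ketamine minus ECT) with a two-sided 95% confidence interval by the Newcombe or score method. The denominator will be stated. P-values, if shown, are descriptive, and a non-significant test is not evidence of similar safety. The SAE risk difference is calculated over the period common to all patients, through the Month 1 contact; later SAEs are described separately.*

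The common window is needed because SAE collection depends on response status. If response rates differ between arms, crude percentages over all collected follow-up would compare unequal observation time.

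The cost is a paragraph of SAP text and a few lines of code on data already collected. The downside is that wide intervals will look less reassuring than a non-significant p-value.

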The sample size justification will be for the primary outcome measure of response rate. Historical data reveal that the overall response rate as well as the respective response rate of ketamine and of ECT is around 50% - 60% on various scale measurements in patients with treatment-resistant depression. Assuming an observed difference of 10% and an acceptable difference margin of 5% with a 1-sided alpha=0.025, a sample of 400 patients (200 per group) provides 81.8% power to detect a treatment response, based on the Farrington-Manning score test of risk difference. The total sample also considers a 10% attrition rate.

10. Study Committees

The following committees will be responsible for the management of the study and the monitoring of the safety of the study patients.

Confidential Page **30** of **40** Protocol V7.0 16Feb2022

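### The protocol and SAP justify the same 400 patients with different attrition rates (10% and 15%), and at 15% the 400 leaves 340 evaluable, not the 346 the SAP says it needs

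*SAP*

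**What the plan says.** **Protocol V7.0, section 9 (Statistical Plan), sample size paragraph.** With a difference of 10 percentage points, a margin of 5 points and one-sided alpha of 0.025, the protocol says that 400 patients (200 per group) "provides 81.8% power to detect a treatment response" on the Farrington-Manning score test. It then adds: "The total sample also considers a 10% attrition rate".

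**SAP V2.0, Sample size justification.** On response rates: "we assume a 50% response rate for ECT patients". For a 10-point margin and a true difference of +5 points, the SAP states: "one-sided alpha value of 0.025, a total sample of 346 is needed to provide 80% power using the Farrington-Manning score test of risk difference". Two further scenarios are given at the same 346. The first reads: "If the actual difference is +10%, the statistical power would increase to 96.4% with the same sample size". The second reduces the margin to 5 points and gives 80.3%. The paragraph closes: "Assuming an attrition rate of 15%, a total number of 400 subjects (200 per treatment group) are then required".

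Both texts are current. The summary of changes at the end of the SAP does not mention attrition, so it does not explain the difference.

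**The concern.** The evaluable number links the randomised total to the stated power, and the two documents imply different evaluable numbers for the same 400: 360 at 10% loss and 340 at 15%. A reader cannot tell which loss the trial was sized for.

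The SAP's own step from 346 to 400 also does not close, because 15% loss from 400 leaves six fewer than the number it calls necessary. At stake is whether the reported justification is reproducible, and whether power is still about 80% at the loss the SAP itself assumes.

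**Working it through.** **Inputs**
- ECT response 50% (SAP, Sample size justification). The protocol gives only a range of 50% to 60%. Taking ECT 50% and ketamine 60% there is an assumption, supported by the fact that it reproduces the protocol's figure.
- One-sided alpha 0.025, critical value 1.96 (both documents).
- 1:1 allocation (Protocol section 5.4).
- Scenario A: margin 10 points, difference +5 (SAP base case).
- Scenario B: margin 5 points, difference +10 (protocol; also the SAP's last scenario).
- Scenario C: margin 10 points, difference +10 (SAP).

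**Formula.** With n per arm, response rates pK and pE, and margin M:

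power = Φ[(pK − pE + M − 1.96·s0) / s1]

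s1 = √{[pK(1−pK) + pE(1−pE)]/n}. s0 has the same form, but uses the maximum-likelihood rates restricted to the null, where ketamine is exactly M below ECT.

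**Step 1: reproduce the SAP at 346 (n = 173).** In scenario A the restricted rates are 0.474 and 0.574, so s0 = √(0.4938/173) = 0.05343 and s1 = √(0.4975/173) = 0.05363. Then (0.15 − 1.96 × 0.05343)/0.05363 = 0.844, and power is 80.1%. Scenarios B and C give 80.3% and 96.4%. All three SAP figures reproduce, and 346 is the smallest total with equal arms that reaches 80% in scenario A.

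**Step 2: reproduce the protocol's 81.8%.** 400 × 0.90 = 360 (n = 180). In scenario B the restricted rates are 0.524 and 0.574, so s0 = √(0.4939/180) = 0.05238 and s1 = √(0.49/180) = 0.05217. Then (0.15 − 1.96 × 0.05238)/0.05217 = 0.907, and power is 81.8%. At the full 400 it would be 85.6%, so the protocol's figure already carries its 10% attrition.

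**Step 3: apply the SAP's 15%.**
- 400 × 0.85 = 340 evaluable (170 per arm), which is 6 short of 346.
- 346/0.85 = 407.1. Per arm, 173/0.85 = 203.5, so 204 per arm and 408 in total.
- 1 − 346/400 = 0.135, so 400 supplies 346 only if attrition is at most 13.5%.

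**Step 4: power at each evaluable number.**

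| Evaluable | A (margin 10, +5) | B (margin 5, +10) | C (margin 10, +10) |
|---|---|---|---|
| 400 (no loss) | 85.4% | 85.6% | 98.1% |
| 360 (10% loss) | 81.6% | 81.8% | 96.9% |
| 346 (SAP requirement) | 80.1% | 80.3% | 96.4% |
| 340 (15% loss) | 79.4% | 79.6% | 96.1% |
| 340, exact enumeration | 80.8% | 79.5% | 96.4% |

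The last row enumerates the binomial outcomes of the same score test. The other rows use the normal approximation, which is the method that reproduces the documents' figures.

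Against the SAP's stated values, the asymptotic shortfalls at 340 are 80 − 79.4 = 0.6, 80.3 − 79.6 = 0.7 and 96.4 − 96.1 = 0.3 points.

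**The case against.** The case for leaving this alone is that the numbers barely move. The gap is 8 randomised patients, or 2% of 400. The SAP's power figures slip by less than one point. By exact enumeration the base case still has 80.8% at 340. The SAP's summary of changes says that version 2 was drafted at the end of the study, so restating power alters neither the sample nor the test. All of this stands, and it is why the point is minor. It does not remove the disagreement between the two attrition rates, or the fact that 400 less 15% is not 346.

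Three stronger readings are tempting, and the documents do not support them.

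- *That the trial fails to deliver its stated power of at least 80%.* The documents state four powers. The 96.4% scenario stays at 96.1%. The base case is below 80% only on the normal approximation. Scenario B is just under 80% by either method, by about half a point.
- *That power falls by 2.2 points, from 81.8% to 79.6%.* This takes a figure calculated with the protocol's 10% loss and applies the SAP's 15% to it. Neither document makes that combined claim, and the protocol's power agrees with its own attrition rate. Within the SAP, the same scenario falls from 80.3% to 79.6%.
- *That the authors multiplied 346 by 1.15 instead of dividing by 0.85.* The product is 397.9, close to 400, but the step is not shown, and 400 is also the protocol's total. The cause is unknown, and the finding does not depend on it.

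**Conclusion.** The inconsistency is real and minor. One sample size rests on 10% attrition in the protocol and 15% in the SAP. The SAP's 400 falls 6 evaluable patients short of its own requirement at its own attrition rate. The consequence is a shortfall of 0.3 to 0.7 points against the SAP's stated powers on the asymptotic method. This does not show that the trial is materially underpowered.

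The conclusion assumes ECT response of 50%, equal loss in the two arms, and attrition that removes patients from the analysed number, which is how both calculations appear to use it.

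The two sample size sections also use different margins for their main calculation (5 points in the protocol, 10 in the SAP). That is a separate and larger matter, and aligning attrition will not settle it.

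**What to change.** Choose one attrition rate, use it in protocol section 9 and in the SAP's Sample size justification, and restate power at the evaluable number it gives:

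- at 15%, 340 evaluable: 79.4% (margin 10, +5), 79.6% (margin 5, +10) and 96.1% (margin 10, +10);
- at 10%, 360 evaluable: 81.6%, 81.8% and 96.9%.

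Alternatively, keep 346 as the requirement and state that 400 randomised supplies it only up to 13.5% attrition, with 408 as the strict requirement at 15%. Say whether the quoted power is asymptotic or exact, since that decides which side of 80% the base case falls on at 340.

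The cost is wording only. If 15% is kept, the stated power becomes slightly less favourable. No patients are added and no analysis changes.
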